3.5.1. Important Protocol Deviations Leading to Exclusion from the PP Population

Deviations from the protocol, as defined in the protocol and/or protocol deviation plan, will be documented by the study monitors and project management throughout the study period.

Only those important protocol deviations considered to have a major effect on efficacy will lead to complete exclusion of the patient from the PP population. For the purposes of this study important protocol deviations leading to exclusion from the PP population will be defined. Criteria which require clinical or medical monitoring interpretation will be reviewed prior to database lock during data review meetings. All important protocol deviations leading to exclusion from the PP population occurring during the study will be reviewed and approved by sponsor prior to database lock in a separate document.

3.6. PK Population

The PK population will consist of all patients who are PK-evaluable, defined as all patients in the ASaT who had at least 1 post-dose concentration measurement above the Lower Limit of Quantification (LLQ).

3.7. Special Subpopulations

Not Applicable.

4. Data Handling

4.1. Time Points and Visit Windows

4.1.1. General Definitions

The study treatment defined is the combination of nanrilefusp alfa 9 µg/kg or 12 µg/kg subcutaneously and 400 mg/m² or 250 mg/m² cetuximab IV infusion.

All assessment days will be related to the first day of first dose of study treatment. Start of study treatment is defined as the date and time of first dose of either nanrilefusp alfa or cetuximab, whichever occurs earliest. Per protocol this should be nanrilefusp alfa.

General Definition	nanrilefusp alfa	Cetuximab
Study Day 1	Day 1 is the first dose of study treatment . Relative days after Day 1 are calculated as (assessment date – Day 1 date) + 1. Relative days prior to Day 1 are calculated as (assessment date – Day 1 date). The day prior to Day 1 is Day -1. Day 0 is not defined.	
Date of the First Dose	As per Exposure CRF (First date from Administration date) Minimum of first dose of nanrilefusp alfa and start date of the infusion for the first dose of cetuximab	As per Exposure CRF (First date from Administration date)
Date of the Last Dose	As per Exposure CRF (Last date from Administration date) Maximum of last dose nanrilefusp alfa and end date of the infusion for the last dose of cetuximab.	As per Exposure CRF (Last date from Administration date)
Treatment Cycle		As per CRF
Treatment Day		As per CRF
Change from baseline		Visit value – baseline value
Percentage change from baseline		100 * (visit value – baseline value) / baseline value

4.1.2. Screening Period

For all patients, the screening period is defined as the period from time of signing ICF to the first dose of treatment (nanrilkefusp alfa or cetuximab) (before day 1 of cycle 1). For some variables, data from more than one assessment within the screening period can be collected prior to the first dose of treatment (nanrilkefusp alfa or cetuximab).

The baseline value is defined as the last non-missing value collected before the first dose of study treatment (nanrilkefusp alfa and/or cetuximab) in the screening period. However, for K-RAS and N-RAS parameters as well as eGFR mutation status which come from Biopsy performed within 3 months prior to first dose will also be considered as baseline values.

4.1.3. Treatment Period

Data collected at Day 1 will be assigned to the Treatment Period unless the time (HH:MM) of data collection and time (HH:MM) of first dose of treatment are both recorded and the data collection time is before the time of first dose of treatment. In this case, the assessment will be assigned to the screening period. If the time (HH:MM) of data collection is not recorded but the protocol and/or eCRF includes an instruction to the effect that all Day 1 assessments are to be performed prior to the first dose of treatment, the data collected at Day 1 will be assigned to the screening period. However, adverse events and medications starting on Day 1, will be assigned to the Treatment Period.

The treatment period is defined from the day of the start of study treatment to the day prior to the end of treatment visit, the end of study date, or start of new anti-cancer therapy, whichever is earliest. Date of last contact collected on the ‘Survival Status’ eCRF where status is ‘dead’ can be after end of study if the contact was with family of subject, but the latest end of study date for a ‘dead’ patient is the death date of the patient.

4.1.4. Visit Windows

All data will be analyzed using nominal study visit as defined in the Study Schedule and eCRF. No visit windows will be applied for summary and analysis except for tumor assessment. Repeated and unscheduled measurements will be included in the listings but not be used for statistical analyses and summaries, except for the derivation of minimum/maximum values post-baseline. All tumor assessments will be considered for the time-to-event analysis.

Unscheduled visits will be identified with a numbering system that reflects the cycle they occur in by comparing the visit date against the scheduled visits and numbering in order of unscheduled visit e.g. Unscheduled Cycle 1 Day 1.01, Unscheduled Cycle 1 Day 8.01 etc. Unscheduled visits occurring on the same day as other visits will not be used in the analysis by timepoint.

Visit window for the Tumor Assessment

Additionally, for the purposes of summarizing target lesions by scheduled week, labels for assessments falling into the scheduled week of study will be derived e.g. ‘Week 6 assessment (Weeks 4 to 8)’, ‘Week 12 assessment (Weeks 10 to 14)’ etc., by assigning the assessments within the protocol specified window of every 6 weeks \pm 2 weeks (e.g. for Week 6 : C1D1 date + 28 \leq Tumor assessment date \leq C1D1 date + 56). Labels for assessments falling outside of the assessment windows would be labelled ‘Not Assigned’. In the case of multiple tumor assessments in a time window, evaluable assessments closest to the planned assessment time (or the closest non-evaluable assessment if all non-evaluable) will be considered the scheduled assessment. In the case of two assessments within a window being exactly the same distance from the centre of the window, the earliest assessment will be assigned as the scheduled assessment. Contributing assessments (e.g. target lesion assessment) should be labelled consistently with the overall tumor assessment.

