8.1.2 Tumor imaging during the study

The first on-study scan assessment should be performed at 6 weeks (± 2 weeks; starting from cycle 1 day 1). Subsequent tumor scans should be performed every 6 weeks (± 2 weeks).

All supplemental imaging must be collected.

Objective response should be confirmed by repeat scan performed at least 4 weeks after the first indication of a response is observed. Patients will then return to the regular scan scheduled, starting with the next scheduled time point. Patients who receive additional scans for confirmation do not need to undergo the next scheduled scan if it is fewer than 4 weeks later; scans may resume at the subsequent scheduled time point.

When radiological disease progression is identified by the investigator in clinically stable patients, disease progression is to be confirmed by another set of scans performed 4 to 8 weeks later, per iRECIST guidelines in section [8.1.5](#).

If disease progression is not confirmed, clinically stable patients are to continue study interventions until progression is confirmed. Patients are to return to their regular scan schedule. If the next scheduled scan will occur in less than 4 weeks, this scheduled scan may be skipped.

If disease progression is confirmed, study interventions will be discontinued. Exceptions are detailed in section [8.1.5](#).

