5.5.6.5. Tumor Burden Analysis

Absolute change from baseline and percent change from baseline for sum of target and new lesion diameters will be summarized in the efficacy population using descriptive statistics for each week of tumor assessment. The best percent change of sum of target and new target lesion will be presented in summary tables.

A waterfall plot of maximum percent reduction in the sum of diameter of target lesions from baseline will be created in the efficacy population. These plots will display the best percentage CFB in the sum of the diameter of all target lesions for each patient.

A spaghetti plot of percent reduction in the sum of target lesions from baseline will be created in the efficacy population to plot the change in tumor burden over time (in weeks from start of treatment) for each patient.

Best percent change from baseline for sum of target lesion diameters is defined as the lowest (minimum) percent change from baseline and will be calculated with one decimal place.

Sum of target lesion diameters will be listed for enrolled population.

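### The ±2-week tumor windows leave 13-day gaps, so an early response confirmed in under 6 weeks can cost that responder one week's value in the exploratory by-week tumor burden table

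*SAP*

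**What the plan says.** Protocol 8.1.2 sets the first on-study scan at 6 weeks from cycle 1 day 1, and then: "Subsequent tumor scans should be performed every 6 weeks", each with ±2 weeks. On confirmation it says: "Objective response should be confirmed by repeat scan performed at least 4 weeks after the first indication of a response is observed". No maximum interval is given. It adds: "Patients who receive additional scans for confirmation do not need to undergo the next scheduled scan if it is fewer than 4 weeks later". Scanning may then resume at the time point after that.

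SAP 4.1.4 turns the ±2 weeks into labels, "for the purposes of summarizing target lesions by scheduled week". The lower bound is written as "for Week 6 : C1D1 date + 28" and the upper bound is C1D1+56. The following window is given as "Week 12 assessment (Weeks 10 to 14" weeks. For everything else: "Labels for assessments falling outside of the assessment windows would be labelled" as *Not Assigned*. If several scans fall in one window, the evaluable scan closest to the planned time is used.

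The labels feed SAP 5.5.6.5, where absolute and percent change in the sum of diameters "will be summarized in the efficacy population using descriptive statistics for each week of tumor assessment".

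**The concern.** The two documents do not fit together. The protocol lets a confirmation scan stand in for the next scheduled scan. The SAP may then give that confirmation scan no week. A patient who followed the protocol exactly can have a valid scan near Week 12 and still be blank in the Week 12 column.

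The blank is not random. Only a patient who has just shown a response (or a progression) gets an off-schedule confirmation scan. The by-week mean is therefore taken over a set selected partly on the outcome being summarized. In a single-arm, proof-of-concept trial, readers will look at this table to judge the depth and timing of tumor shrinkage.

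**Working it through.** **Inputs.** From the documents: nominal scan days C1D1+42, +84, +126 (Protocol 8.1.2); windows of nominal day ±14, inclusive (SAP 4.1.4); confirmation at least 28 days after first response (Protocol 8.1.2), or more than 4 weeks apart in the BOR algorithm (SAP 5.5.3.1); next scheduled scan skippable if fewer than 28 days away (Protocol 8.1.2).

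**Step 1: reproduce the windows and find the gaps.** Week 6: 42 ± 14 = +28 to +56. Week 12: 84 ± 14 = +70 to +98. Both match the SAP. Week 18: 126 ± 14 = +112 to +140. Gap length = next start - previous end - 1 = 70 - 56 - 1 = 13 days (+57 to +69). The next gap is +99 to +111, also 13 days. So 13 of every 42 days have no week.

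**Step 2: the skip.** A scan on +57 is 84 - 57 = 27 days before the Week 12 scan, and one on +69 is 84 - 69 = 15 days before it. Both are under 28, so the skip is allowed for every scan in the gap.

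**Step 3: who lands in the gap.** Let d be the day of first response in the Week 6 window (29 possible days) and k the days to confirmation. The gap is hit when 57 ≤ d + k ≤ 69.

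| k (days) | First-response days that hit the gap | Share of the 29 days |
|---|---|---|
| 28 | +29 to +41 | 13/29 = 45% |
| 29 | +28 to +40 | 13/29 = 45% |
| 35 | +28 to +34 | 7/29 = 24% |
| 42 | none | 0/29 |

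A response seen on the nominal day +42 and confirmed 28 days later falls on +70, the first day of Week 12, and is assigned. The gap is hit only if the first response scan is before its nominal day **and** confirmation comes in under 42 days. Example: PR on +36, confirmation on +64 (*Not Assigned*), scan on +84 omitted because it is 20 days away. Week 12 is then empty, and the patient returns at +126 in Week 18.

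**Step 4: illustrative size.** The documents give no distribution of scan dates or tumor changes, so these are assumed: 36.8% responders (the plan's desired ORR) at -45%, all others at +5%, first response at the first scan, every response confirmed by a dedicated scan, every allowed skip taken, no non-responder missing.

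Without loss: 0.368 × (-45) + 0.632 × 5 = -16.56 + 3.16 = -13.4%.

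With a share L of responders missing: mean = [0.368(1 - L)(-45) + 0.632 × 5] / [0.368(1 - L) + 0.632].

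At L = 13/29: (-9.14 + 3.16) / (0.203 + 0.632) = -7.2%.

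| Confirmation delay | L, first scan uniform on +28 to +56 | L, first scan normal (mean +42, SD 5) | Mean at Week 12 |
|---|---|---|---|
| 28 days | 45% | 46% | -7.2% / -7.0% |
| 28 to 35 days, equally likely | 36% | 23% | -8.6% / -10.4% |
| 28 to 42 days, equally likely | 24% | 13% | -10.4% / -11.8% |

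If half the skips are taken, L halves: at 28 days the mean is about -10.5%, and over 28 to 42 days it is -11.9% to -12.6%.

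**Step 5: losses on the other side.** If 20% or 30% of non-responders also lack Week 12 while L = 45%, the mean is (-9.11 + 2.53)/(0.202 + 0.506) = -9.3%, or (-9.11 + 2.21)/(0.202 + 0.442) = -10.7%, instead of about -7.2%.

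**Step 6: what contiguous windows alone achieve.** With Week 6 = +22 to +63, confirmation scans on +57 to +63 become Week 6, and Week 12 stays empty if the scheduled scan is skipped. At k = 28 that is d = +29 to +35: 7/29 = 24% under the uniform assumption and 9% under the normal one, against 45-46% before.

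**The case against.** The strongest reply is that the windows simply mirror the protocol's own ±2 weeks and touch very little. That is largely right. The labels serve only the by-week target lesion summaries. SAP 5.5.3.1 derives BOR, and hence ORR, from scheduled and unscheduled scans alike. SAP 4.1.4 uses all tumor assessments for time-to-event analyses and keeps unscheduled values for minimum and maximum derivations, so best percent change and the waterfall plot stand. The spaghetti plot runs on weeks from start of treatment. The futility rule does not use the by-week mean.

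A reader might infer that 4-week confirmation scans in general fall into the gaps and that responders drop out of the tumor burden summaries. The documents do not support that. On-time or late first scans put the confirmation scan in the next window, and a routine 6-week scan used as confirmation is never lost. An affected responder keeps the response week, usually loses one column and returns at the next scheduled scan.

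Nor is the labelling rule the sole cause. Week 12 is empty only if the optional skip is taken. A reader might also infer a known bias against the drug. Progression is likewise confirmed by a repeat scan 4 to 8 weeks later, with a skip allowed if it is not confirmed and treatment normally stopped if it is. Those losses push the mean the other way.

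Finally, a confirmation at exactly 28 days would not meet a strict reading of the SAP's more-than-4-weeks rule. At 29 days the uniform share is unchanged at 45%, and the normal share is 38%.

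What remains is that following both documents as written can blank a week despite a valid nearby scan, and that the blank depends on outcome.

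**Conclusion.** The point holds in limited form. The 13-day gaps and the universal skip option for scans inside them follow directly from the two documents. A responder first seen before the nominal day and confirmed in under 6 weeks can lose one week's value in an exploratory, descriptive table.

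Under the stated assumptions the loss at Week 12 is 13-46% of responders, with the mean moving from -13.4% to between -11.8% and -7.0%. The loss is about half that if half the skips are taken. These are scenarios, not forecasts. They count responders only, and progression-related losses make the net direction uncertain. No primary or secondary endpoint changes. This is a cheap improvement, not a flaw in the main analysis.

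**What to change.** For the by-week summaries only, amend SAP 4.1.4 as follows:

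- Assign each scan to the nearest nominal week in contiguous 42-day blocks: Week 6 = C1D1+22 to +63, Week 12 = +64 to +105, and so on. Keep the existing closest-evaluable rule for multiple scans.
- State that a confirmation scan replacing a skipped scheduled scan takes that scan's week label. Contiguous windows alone are only a partial remedy (Step 6).
- State that such scans count in the by-week summary. SAP 4.1.4 currently excludes repeated and unscheduled measurements from summaries, yet assigns tumor scans by date.

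The cost is two sentences and revised window bounds. The scan schedule is unchanged and no data are discarded. The downside is that some values will lie further from their nominal week: about 3 weeks under the contiguous windows, and up to 84 - 57 = 27 days (nearly 4 weeks) for a relabelled confirmation scan.

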4.2. Handling of Dropouts, Missing Data, and Outliers

4.2.1. Handling of Missing Efficacy Data

Patients with missing data for the efficacy endpoints of ORR, iORR, CBR and iCBR will be classified as non-responders, if not otherwise specified.

Patients with missing data for the efficacy endpoints of DoR, iDoR, PFS, iPFS, TtR, iTtR, TtP, iTtP, PFS2, and OS at the end of trial will be regarded as censored as described in [Section 5.5.3](#).

4.2.2. Handling of Missing Safety Data

In general, missing clinical laboratory data, vital signs, and Electrocardiogram (ECG) data will not be imputed. Unknown or partial medication and AE date imputations are given below and to be used only for the assessment of prior / concomitant status for medications and treatment-emergent status for AEs.

4.2.3. Handling of Partial and Missing Dates for Adverse Events, Prior / Concomitant Medications/Procedures

Missing or Partial Adverse Event and Prior / Concomitant Medication/Procedure Start Dates

Missing and / or incomplete dates for medications, procedures and AEs are imputed in a manner resulting in the earliest onset or the longest duration during the Treatment Period, whilst ensuring that the start date does not occur after the stop date. The stop date will not be imputed if the medication or AE is “Ongoing”. Technically, this will be done as follows:

For a missing/incomplete start date/time the earliest date/time of the following will be imputed:

- The later date of: the earliest possible start date / time, and the date / time of first dose of treatment.
- The latest possible start date/time.
- The latest possible stop date/time.

For a missing/incomplete stop date/time the later date/time of the following will be imputed:

- The earlier date/time of the latest possible stop date/time and the date/time of last dose of treatment.
- The earliest possible stop date/time.
- The earliest possible start date/time.

Here, the earliest possible date/time is defined as:

- The date/time itself if available.
- The date/time of the first day of the month at 00:00hrs, if month and year are available but the day/time is missing.
- The date/time of the first day of the year at 00:00hrs, if year is available but day/time and month are missing.
- 00:00hrs on the day of informed consent, if the date/time is completely missing.

The latest possible date/time is defined as:

- The date/time itself if available.
- The date/time of the last day of the month at 23:59hrs, if month and year are available but the day/time is missing.
- The date/time of the last day of the year at 23:59hrs, if year is available but day/time and month are missing.
- 23:59hrs on the date of last known date on the study for the patient plus one year, if the date/time is completely missing.

4.2.4. Handling of Partial and Missing Dates for New Anti-Cancer Therapy

Incomplete start dates of follow-up anti-cancer therapy will be imputed as follows:

If only 'day' is missing, then impute with the first day of the month.

If 'day' and 'month' are missing and 'year' is not missing and equal to year of last dose, then impute as date of last dose.

Else if 'day' and 'month' are missing and 'year' is not missing and before year of last dose, then impute as 31st December of that year.

Else if 'day' and 'month' are missing and 'year' is not missing and after year of last dose, then impute as 1st January of that year.

If the imputed start date is greater than the last contact date, then set to the last contact date.

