4.2.5. Handling of Partial and Missing Death Date

Incomplete dates of death will be imputed as follows:

If only ‘day’ is missing, then impute with the first day of the month.

If ‘day’ and ‘month’ are missing and ‘year’ is not missing and is the same as the year of the last contact date, then impute as the date of the last contact +1 day.

If ‘day’ and ‘month’ are missing and ‘year’ is not missing and is greater than the year of the last contact date, then impute as 1st January of that year.

If the imputed death date is less than the last contact date, then set to the last contact date + 1 day.

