5.5. Efficacy

Only tumor assessments prior to or at the date of initiation of further-line therapy and using CT scan or MRI will be used for the evaluation of tumor response.

In case of a confirmed response or disease progression, the date of the first tumor assessment evaluated as response or progression will be used for the time-to-event variables.

Up to the first iUPD, the RECIST 1.1 disease response assessment will be derived from the iRECIST response assessment form as follows:

Table 2 Derivation of RECIST 1.1 Disease Response from iRECIST 1.1

iRECIST	RECIST 1.1
iCR	CR
iPR	PR
iSD	SD
iUPD	PD
Non-iCR/Non-iUPD	Non-CR / Non-PD
NE	NE

After the first iUPD, the RECIST 1.1 overall response will no longer be derived.

All efficacy data endpoint will be listed on the enrolled population, with the exception of time to event analyses where the ASaT population will be used.

Overview of Tumor Assessments with a swimmer plot per RECIST 1.1 and iRECIST 1.1 will be displayed graphically for ASaT population.

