5.5.3.3. DoR and iDoR

The DoR and iDoR are defined as the time until progression of disease or death for patients with PR, iPR or CR, iCR and will be summarized using Kaplan-Meier estimates in the efficacy population. Responders will be considered to have an ongoing response if they:

- have not progressed, and
- have not started a next-line anti-cancer therapy, and
- have not been lost to follow-up, and
- are alive.

Patients with missing data will be censored/considered as having an event as specified in the table below.

Table 4 DoR and iDoR events and censoring

Situation	Date of progression or censoring	Outcome
No progression, no death. No start of next-line anti-cancer therapy.	Date of the last evaluable tumor assessment.	Censored
No progression, no death. Start of next-line anti-cancer therapy.	Date of the last tumor assessment with non-progression before the start of next-line anti-cancer therapy.	Censored
Progression or death after one missed adequate tumor assessment.	Date of progression or death, whichever is earliest (if both occur).	Progressed
Progression or death after more than one missed adequate tumor assessment.	Date of the last evaluable tumor assessment.	Censored

For DOR, the start date is the date of first documented response of CR or PR (i.e. the start date of response, not the date when response was confirmed), and the end date is defined as the date of the first documented progression or death.

For iDOR, the start date is the date of first documented response of iCR or iPR (i.e. the start date of response, not the date when response was confirmed), and the end date is defined as the date of the first documented progression according to iRECIST or death.

The progression date to be used for calculation of iDOR should be the first date at which progression criteria are met (i.e, the date of iUPD) provided that iCPD is confirmed at the

next assessment. If iUPD occurs, but is disregarded because of later iSD, iPR, or iCR, that iUPD date should not be used as the progression event date.

If progression is not confirmed and there is no subsequent iSD, iPR, or iCR, the iUPD date should still be used if:

- the patient stops protocol treatment because they were not judged to be clinically stable, or
- no further tumor assessments are done, or
- the next timepoint responses are all iUPD, and iCPD never occurs, or
- the patient dies from his cancer.

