5.5.3.5. PFS and iPFS

PFS and iPFS are defined as the time from the first day of study treatment until the first date of radiological disease progression or death and will be summarized using Kaplan-Meier estimates in the efficacy population.

Patients with missing data will be censored/considered as having an event as specified in the table below.

Table 5 PFS and iPFS events and censoring

Situation	Date of progression or censoring	Outcome
Incomplete or no baseline tumor assessment.	First day of study treatment	Censored

Start of next-line anti-cancer therapy.	Date of the last tumor assessment with non-progression before the start of next-line anti-cancer therapy.	Censored
Death before the first disease progression assessment.	Date of death.	Progressed
Death between adequate tumor assessment visits.	Date of death.	Progressed
Progression or death after one missed adequate tumor assessment.	Date of progression or death, whichever is earliest (if both occur).	Progressed
Progression or death after more than one missed adequate tumor assessment.	Date of the last evaluable tumor assessment.	Censored
No progression, no death.	Date of the last evaluable tumor assessment.	Censored

For iPFS, the progression date to be used for calculation should be the first date at which progression criteria are met (i.e, the date of iUPD) provided that iCPD is confirmed at the next assessment. If iUPD occurs, but is disregarded because of later iSD, iPR, or iCR, that iUPD date should not be used as the progression event date.

If progression is not confirmed and there is no subsequent iSD, iPR, or iCR, the iUPD date should still be used if:

- the patient stops protocol treatment because they were not judged to be clinically stable, or
- no further tumor assessments are done, or
- the next timepoint responses are all iUPD, and iCPD never occurs, or
- the patient dies from his cancer.

PFS according to RECIST and iRECIST will be listed for ASaT population.

PFS according to RECIST and iRECIST will be displayed graphically using Kaplan-meier plots for efficacy and ASaT populations including count for numbers of patients at risk.

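### SAP 4.2.4 sets a next-line start with a missing day to the 1st of the month with no floor, so a same-month progression scan can be dropped and a RECIST PFS, TtP or DoR event censored

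*SAP*

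**What the plan says.** - SAP 4.2.4, day missing: "then impute with the first day of the month". The one bound is "If the imputed start date is greater than the last contact date, then set to the last contact date".
- SAP 4.2.4, day and month missing: if the year "is not missing and equal to year of last dose, then impute as date of last dose".
- SAP 4.2.5, partial death date, does have a floor: "If the imputed death date is less than the last contact date, then set to the last contact date + 1 day".
- SAP 5.5, and the same rule in Protocol 9.3.1: "Only tumor assessments prior to or at the date of initiation of further-line therapy and using CT scan or MRI will be used" for evaluating tumor response.
- SAP Table 5 (PFS, iPFS) censors a patient who starts next-line therapy at "Date of the last tumor assessment with non-progression before the start of next-line anti-cancer therapy". Table 6 (TtP, iTtP) has the same row. Neither row is limited to patients without progression.
- SAP Table 4 (DoR, iDoR) has a next-line row that is limited in this way: "No progression, no death. Start of next-line anti-cancer therapy".
- SAP 4.1.4, on visit windows and unscheduled visits, says that all tumor assessments count in the time-to-event analysis. It does not mention next-line therapy.

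**The concern.** The imputed date decides whether a progression scan is used, and the 1st of the month is the earliest date the record allows. If a patient progresses and changes treatment within one calendar month, the imputed start falls before the progression that led to the change. An observed event then becomes a censored time.

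For the progression endpoints the error has one direction, and a single-arm trial has no control arm to carry the same bias. The rule can also date next-line therapy before the last study dose, although Protocol 6.8.2 prohibits other anti-cancer therapy during study treatment.

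**Working it through.** The plan gives no figure to reproduce, so the rules were applied in order and the exposure then counted.

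**Worked case.** Progression scan on 10 May; next-line therapy truly started on 25 May, recorded only as May.
1. SAP 4.2.4 gives a start of 1 May.
2. The scan of 10 May is later than 1 May, so SAP 5.5 excludes it.
3. PFS and TtP are censored at the last non-progression scan before 1 May. Scans are 6 weeks apart, ±2 (Protocol 8.1.2), so this is about 6 weeks earlier. For DoR, no progression is left on file, so the Table 4 row applies.
4. With the true date, all are events on 10 May.
5. If that was the only post-baseline scan, BOR moves from PD to NE (SAP 5.5.3.1).

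**Share of scans lost, given a missing day.** Let g be the days from progression scan to true start. In a month of L days, a scan on day d is lost if d ≥ 2 (a scan on the 1st is kept, because scans at the start date are used) and d + g ≤ L. That is L − g − 1 days, or zero if negative. Over an average year of 365.25 days, for g up to 27, the share is 1 − 12(g + 1)/365.25.
- g = 7: 1 − 96/365.25 = 73.7%
- g = 14: 1 − 180/365.25 = 50.7%
- g = 21: 1 − 264/365.25 = 27.7%
- g = 28: seven 31-day months give 2 days each and four 30-day months 1 day each, so 18/365.25 = 4.9%
- g = 29: 7/365.25 = 1.9%
- g ≥ 30: 0%, since the longest possible gap is from the 2nd to the 31st

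Enumerating all 1,461 progression dates in 2023–2026 gives the same values at 7, 14, 21 and 28 days, and 0% at 35.

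**Size in this trial (illustration).** N = 52 is from SAP 2.3. The rest is assumed: all 52 progress, 60% start next-line therapy 3 to 28 days later (uniform), and the underlying median is 3 or 5 months. The mean share lost over those gaps is (25 − 12 × 400/365.25 + 0.049)/26 = 0.458. Expected events lost = 52 × 0.60 × 0.458 × rate = 14.3 × rate. A simulation gave the Kaplan-Meier medians.

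| Missing-day rate | Events lost | Median, 3-month case | Median, 5-month case |
|---|---|---|---|
| 5% | 0.7 | 3.70 → 3.74 | 5.67 → 5.75 |
| 10% | 1.4 | 3.71 → 3.79 | 5.68 → 5.87 |
| 20% | 2.9 | 3.71 → 3.86 | 5.63 → 5.96 |
| 40% | 5.7 | 3.70 → 4.03 | 5.72 → 6.35 |

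**Which floor works.** A floor at last dose alone is not enough. With the last dose 7 days before the progression scan, the shares lost stay at 73.7% (g = 7) and 50.7% (g = 14). With a floor at the last scan of the month, the share is 0%.

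**The case against.** **The usual pathway keeps the gap long.** Protocol 8.1.2 and 10.2.2 keep clinically stable patients on treatment after RECIST progression until a repeat scan 4 to 8 weeks later, while SAP 5.5 dates the event at the first progression scan. Their gap is normally at least 28 days, where the share lost is 4.9% or less. This stands. The larger shares apply to patients who stop and switch before confirmation. Nothing in the documents shows that most patients switch quickly, so the 60% in the illustration is on the high side.

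**iRECIST endpoints are partly protected.** If a confirming scan is lost, SAP 5.5.3.3, 5.5.3.5 and 5.5.3.7 still use the iUPD date when, for example, no further assessments are done. This stands where the iUPD scan itself is kept.

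**The text may not require the exclusion.** Tables 4 to 6 are introduced for patients with missing data, SAP 5.5 speaks of tumor response, and SAP 4.1.4 counts all assessments. This does not clearly rescue the scan. Once SAP 5.5 removes it, no progression is on file, and SAP 4.1.4 states no exception to that cut-off. The sections should be reconciled.

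**Stronger readings.**
- A reader might infer that every efficacy endpoint is biased in the drug's favor. PD and NE are both non-response, so ORR does not rise; a lost same-month confirmatory scan could turn PR into SD and lower it.
- A reader might infer that the year-only rule loses end-of-treatment scans in general. It is anchored at last dose and loses only progression scans taken after that dose.
- A reader might infer an effect on adverse-event counts, because SAP 4.1.3 ends the treatment period at new therapy. The treatment-emergent definition in SAP 5.6.3 has no end date.

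**Conclusion.** The gap is real and small. Followed as written, the SAP turns an observed progression into censoring when three things coincide: the day of next-line start is missing, the progression scan falls in the same calendar month as the true start, and that scan is not on the 1st. RECIST PFS and TtP are affected through SAP 5.5 and Tables 5 and 6, and DoR through the SAP 5.5 cut-off.

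The exposed patients are mainly those who switch within about 4 weeks of first progression. The loss of about 1 of 52 PFS events, with a median shift of 0.04 to 0.19 months, rests on assumed missing-day rates of 5 to 10% and on the assumed switching pattern. These endpoints are secondary and descriptive. The point does not threaten the primary result, but it is worth closing before database lock.

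**What to change.** In SAP 4.2.4:
- **Day missing:** impute the latest of the 1st of the month, the day after the last study dose, and the date of the last on-study tumor assessment in that month, whatever its result. Cap at month end and at last contact.
- **Day and month missing, same year as last dose:** use the later of last dose and the last on-study tumor assessment in that year, with the same last-contact cap.

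The scan floor must not depend on the scan's result. If it applied only to scans showing progression, the imputed date would depend on the outcome and could create events that the plan means to censor. A result-neutral floor fits Protocol 8.1.3, where study scans stop at next-line start.

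Also state that SAP 4.1.4 does not override the SAP 5.5 cut-off, and give the next-line rows of Tables 5 and 6 the no-progression condition that Table 4 has, so that a progression scan on the imputed start date counts as an event.

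The cost is a few sentences of SAP text and a small code change. The downside is that a scan truly taken after next-line start in that month would be counted, which the imaging schedule makes unlikely.
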